7.10 Efficacy, Immunogenicity, Pharmacokinetic, and Pharmacodynamic Assessments

7.10.1 Efficacy Assessments

7.10.1.1 Radiologic Evaluation: Treatment of Patients According to Principles of Immune-Related Response Criteria

Tumor assessments will be obtained at screening using CT and/or MRI scans at time intervals as specified in the [Appendix 1](#) and [Appendix 2](#) (Time and Events Tables). Radiographic disease assessments will occur every 6 weeks (i.e., following 2 cycles of treatment [specifically prior to Cycles 3, 5, 7, etc.]) for the first 24 weeks and then every 12 weeks thereafter until documented progression, initiation of alternative anti-cancer therapy, lost to follow up, withdrawal of informed consent, death, or end of study. Treatment will continue until patients have completed study therapy and required follow-up, experienced disease progression according to irRC, or have been withdrawn from the study (see [Section 4.4](#) and [Section 5.3](#)). At each on-treatment tumor assessment time point, the objective response status will be determined. In the context of the statistical analysis for this trial, objective response determination and the assessment of best overall response (BOR) will be defined using both conventional RECIST 1.1 criteria ([Appendix 7](#)) as well as an adaptation of these criteria, designated as immune-related response criteria (irRC) ([Appendix 8](#)). Patient management decisions, however, will be made solely based on the immune-related response criteria.

For patients who demonstrate acceptable tolerability of treatment with pembrolizumab and margetuximab and achieve an objective response assessment of irCR, irPR or irSD, or unconfirmed clinically stable irPD, therapy may be continued (see [Section 4.4](#) and [Section 5.3](#)).

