For patients who are otherwise clinically stable, but have met conventional criteria for PD, therapy may be continued at the discretion of the investigator pending confirmation of progression at the next scheduled tumor assessment. This approach allows for limited treatment of patients beyond the initial radiographic documentation of disease progression, assuming that patients are tolerating therapy adequately, that patients remain otherwise clinically stable despite this initial radiographic evidence of disease progression, and that the investigator feels the patient may still derive benefit from continuation of therapy. Treatment of patients according to irRC principles is supported by well-documented evidence that in some patients treated with T cell directed, immune-modulatory agents, their tumors can evolve to an objective response after an initial period characterized by either apparent radiographic growth of target lesions or the development of new target lesions that would otherwise meet the criteria for disease progression using conventional response criteria ([Appendix 7](#)).

For patients in whom progression is confirmed at the next scheduled tumor assessment, the criteria for immune-related PD (irPD) will have been met, and treatment with margetuximab and pembrolizumab should be discontinued. The patient should be removed from study participation after completion of protocol specified follow-up (see [Section 8.3](#) and [Appendix 1](#) and [Appendix 2](#)). For patients who experience an objective response of immune-related complete response (irCR) or immune-related partial response (irPR), responses will be considered unconfirmed until the response has been documented by a subsequent confirmatory scan obtained no less than 4 weeks after the initial scan demonstrating an objective response.

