- 12 Samples will be analyzed by the local laboratory.
- 13 Includes ALB, ALK-P, ALT, AST, amylase, bicarbonate, BUN, Ca, Cl, creatinine, glucose, lipase, magnesium, phosphorus, K, Na, total protein, uric acid, total and direct bilirubin.
- 14 For Cytokine samples: Samples can be obtained selectively at additional time points in patients who experience an adverse event with signs and symptoms of cytokine release, with the goal to obtain a cytokine sample immediately at the time of onset of adverse event. Multiple cytokine samples can be drawn for any specific adverse event that is suspected to be due to cytokine release, as clinically indicated; specific date and times of blood draws must be recorded. Separate cytokine samples should be drawn for each adverse event suspected of cytokine release, with specific date and time of draw to be recorded.
- 15 Vital signs include temperature, pulse, blood pressure, and respiratory rate and are obtained as follows:
 - In relation to pembrolizumab infusions on Days 1: Vital signs will be taken immediately before the pembrolizumab infusion (up to 5 minutes before the infusion [pre-dose]); at 15 minutes after the start of infusion; at 30 minutes (end of infusion), and at 1 hour after infusion if the margetuximab dose has not already commenced.
 - In relation to margetuximab infusions on Days 1: Vital signs will be taken immediately before margetuximab infusion (up to 5 minutes before the infusion [pre-dose]), at 60 minutes after start of infusion, at 120 minutes (end of infusion), and at 1 hour after the completion of infusion.
 - Note: For subsequent cycles after Cycle 1; the 1-hour post-infusion vital signs measurements may be deferred if continuing monitoring is not clinically indicated.
- 16 Radiographic disease assessments will occur every 6 weeks (i.e., following 2 cycles of treatment) for the first 24 weeks and then every 12 weeks thereafter until documented progression, initiation of alternative anti-cancer therapy, lost to follow up, withdrawal of informed consent, death, or end of study. To be performed within 3 days prior to dosing on Day 1 of every other cycle for the first 24 weeks (specifically prior to Cycles 3, 5, 7, and 9) and then every 4th cycle (prior to Cycles 13, 17, 21, etc.). Disease assessment will be done at office follow-up visits until end of study if patient agrees.

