All other lesions (or sites of disease) including pathological lymph nodes should be identified as *non-target lesions* and should also be recorded at baseline. Measurements are not required and these lesions should be followed as ‘present’, ‘absent’, or in rare cases ‘unequivocal progression. In addition, it is possible to record multiple non-target lesions involving the same organ as a single item on the case record form (e.g. ‘multiple enlarged pelvic lymph nodes’ or ‘multiple liver metastases’).

RESPONSE CRITERIA

This section provides the definitions of the criteria used to determine objective tumor response for target lesions.

Evaluation of target lesions

Complete Response (CR): Disappearance of all target lesions. Any pathological lymph nodes (whether target or non-target) must have reduction in short axis to < 10 mm.

Partial Response (PR): at least a 30% decrease in the sum of diameters of target lesions, taking as reference the baseline sum diameters.

Progressive Disease (PD): at least a 20% increase in the sum of diameters of target lesions, taking as reference the *smallest sum on study* (this includes the baseline sum if that is the smallest on study). In addition to the relative increase of 20%, the sum must also demonstrate an absolute increase of at least 5 mm. (*Note*: the appearance of one or more new lesions is also considered progression).

Stable Disease (SD): Neither sufficient shrinkage to qualify for PR nor sufficient increase to qualify for PD, taking as reference the smallest sum diameters while on study.

Special notes on the assessment of target lesions

Lymph nodes. Lymph nodes identified as target lesions should always have the actual short axis measurement recorded (measured in the same anatomical plane as the baseline examination), even if the nodes regress to below 10 mm on study. This means that when lymph nodes are included as target lesions, the ‘sum’ of lesions may not be zero even if complete response criteria are met, since a normal lymph node is defined as having a short axis of <10 mm. In order to qualify for CR, each node must achieve a short axis <10 mm. For PR, SD and PD, the actual short axis measurement of the nodes is to be included in the sum of target lesions.

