If a new lesion is equivocal, for example because of its small size, continued therapy and follow-up evaluation will clarify if it represents truly new disease. If repeat scans confirm there is definitely a new lesion, then progression should be declared using the date of the initial scan.

EVALUATION OF BEST OVERALL RESPONSE

The best overall response is the best response recorded from the start of the study treatment until the end of treatment taking into account any requirement for confirmation. The patient’s best overall response assignment will depend on the findings of both target and non-target disease and will also take into consideration the appearance of new lesions.

Time point response

It is assumed that at each protocol specified time point, a response assessment occurs. **Table A-1** on the next page provides a summary of the overall response status calculation at each time point for patients who have measurable disease at baseline.

Missing assessments and inevaluable designation

When no imaging/measurement is done at all at a particular time point, the patient is not evaluable (NE) at that time point. If only a subset of lesion measurements are made at an assessment, usually the case is also considered NE at that time point, unless a convincing argument can be made that the contribution of the individual missing lesion(s) would not change the assigned time point response. This would be most likely to happen in the case of PD. For example, if a patient had a baseline sum of 50 mm with three measured lesions and at follow-up only two lesions were assessed, but those gave a sum of 80 mm, the patient will have achieved PD status, regardless of the contribution of the missing lesion.

Best overall response: all time points

The *best overall response* is determined once all the data for the patient is known.

Table A-1 Time point response: patients with target (+/- non-target) disease

Target lesions	Non-target lesions	New lesions	Overall response
CR	CR	No	CR
CR	Non-CR/non-PD	No	PR
CR	Not evaluated	No	PR
PR	Non-PD or not all evaluated	No	PR
SD	Non-PD or not all evaluated	No	SD
Not all evaluated	Non-PD	No	NE
PD	Any	Yes or No	PD
Any	PD	Yes or No	PD
Any	Any	Yes	PD

CR = complete response, PR = partial response, SD = stable disease, PD = progressive disease, and NE = inevaluable.

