#### 5.1.2 Time to Event Endpoints

- Progression-free survival (PFS): The PFS is defined as the time from the first dose date to the date of first documented progression or death from any cause, whichever occurs first. For patients who are not known to be dead or progressed at the time of data cut-off for PFS analysis, the PFS will be censored at the date of the last tumor assessment. The documented progression is determined by radiographic assessment using RECIST v1.1. PFS will be calculated as:

$$\text{PFS (months)} = (\text{date of event [documented progression or death] or date of censoring} - \text{first dose date} + 1) / (365.25/12)$$

- Duration of response (DoR): The DoR is defined as the time from the date of initial response to the date of first documented progression or death from any cause, whichever occurs first. DoR will be analyzed for responding patients only. For responding patients who are not known to be dead or progressed at the time of data cut-off for DoR analysis, the DoR will be censored at the date of the last tumor assessment. The documented progression is determined by radiographic assessment using RECIST v1.1. DoR will be calculated as:

$$\text{DoR(months)} = (\text{date of event [documented progression or death] or date of censoring} - \text{date of initial response} + 1) / (365.25/12)$$

DoR may also be determined by irRECIST.

- Overall survival (OS): The OS is defined as the time from the first dose date to the date of death from any cause. For patients who are not known to be dead at the time of data cut-off for OS analysis, the OS will be censored at the time they are last known to be alive. OS will be calculated as:

$$\text{OS (months)} = (\text{date of death or last known alive} - \text{first dose date} + 1) / (365.25/12)$$

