### **6.6 Efficacy Endpoint Analyses**

#### **6.6.1 Analyses of Response Endpoints**

The objective response rate (ORR) is estimated as the proportion of patients in the response evaluable population achieving a CR or PR per RECIST v1.1. A two-sided 95% exact binomial CI for ORR will be calculated. In addition, the ORR per irRECIST and its 95% CI will also be calculated.

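### RECIST 1.1 best overall response is not cut off at RECIST 1.1 progression, so shrinkage after progression by target-lesion growth can count as a confirmed response

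*Protocol*

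**What the plan says.** Protocol 7.10.1.1 ties the statistical analysis to the appendices: "objective response determination and the assessment of best overall response (BOR) will be defined using both conventional RECIST 1.1 criteria" (Appendix 7) and the immune-related criteria (Appendix 8). Appendix 7 then sets the window: "The best overall response is the best response recorded from the start of the study treatment until the end of treatment". The sentence goes on to mention any confirmation requirement and does not mention progression. Appendix 8 uses the same window for the immune-related criteria.

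The SAP adds no cut. Section 5.1.1 requires CR and PR to be confirmed at least 28 days later, and section 6.6.1 counts patients "achieving a CR or PR per RECIST v1.1".

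Treatment does not stop at conventional progression. Under Protocol 4.1.1 and 7.10.1.1, for clinically stable patients "therapy may be continued at the discretion of the investigator pending confirmation of progression at the next scheduled tumor assessment". The stated reason is that in some patients "their tumors can evolve to an objective response after an initial period characterized by either apparent radiographic growth of target lesions".

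Partial response in Appendix 7 is "at least a 30% decrease in the sum of diameters of target lesions, taking as reference the baseline sum diameters". Duration of response in SAP 5.1.2 is "the time from the date of initial response to the date of first documented progression or death from any cause", with progression judged by RECIST 1.1.

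**The concern.** If treatment ended at RECIST 1.1 progression, a window running to end of treatment would do little harm. In this trial, end of treatment can fall well after RECIST 1.1 progression. The protocol also expects some patients to shrink after apparent growth, and it offers the immune-related criteria as the way to capture them. Without a cut, the conventional ORR can take in the same patients.

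ORR and response duration by RECIST 1.1 belong to a primary objective (Protocol 3.1, SAP 2.1). A patient could be a RECIST 1.1 responder in one table, an earlier RECIST 1.1 PFS event in another, and carry a negative duration in a third. Two programmers working from the same data could also report different RECIST 1.1 ORRs, because the text does not settle the case.

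**Working it through.** **Step 1. Apply the rules to one patient.** The lesion sums are illustrative: baseline 100 mm and no new lesions. Scans are those before Cycles 3, 5 and 7; Protocol Table 5 places Day 1 of these cycles on study days 43, 85 and 127.

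| Scan | Sum (mm) | Change from baseline | Table A-1 result |
|---|---|---|---|
| Week 6, day 43 | 122 | +22% (+22 mm, so the 5 mm minimum is met) | PD |
| Week 12, day 85 | 65 | -35% | PR |
| Week 18, day 127 | 60 | -40% | PR |

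- PR is judged against baseline, so the earlier PD does not prevent it.
- The two PR scans are 127 - 85 = 42 days apart, which meets the 28-day rule.
- Table A-2 gives PR for PR followed by PR. It has no row that starts with PD, so nothing removes the response.
- The progression is not confirmed at week 12, so treatment may have continued and all three scans lie inside the window.

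The literal best overall response is a confirmed RECIST 1.1 PR.

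**Step 2. Apply the SAP 5.1.2 time-to-event formulas to the same patient**, with 365.25/12 = 30.44 days per month.

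- PFS = (43 - 1 + 1)/30.44 = 1.41 months, with an event at week 6.
- DoR = (43 - 85 + 1)/30.44 = -41/30.44 = -1.35 months.

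**Step 3. Find the limit.** The last row of Table A-1 makes any time point with a new lesion PD, whatever the target lesions do. A patient who progresses by a new lesion that persists stays at PD and cannot become a responder. The exposure is confined to progression by target-lesion growth, or other progression without a persisting new lesion.

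**Step 4. Size.** The plan uses exact binomial limits: lower = Beta quantile at 0.025 with parameters (x, n-x+1), upper = Beta quantile at 0.975 with parameters (x+1, n-x). This reproduces the intervals in Protocol Table 7 and SAP Table 1, for example 5/30 = 16.7% (5.6 to 34.7) and 6/25 = 24% (9.4 to 45.1). Counting one or two extra patients, an assumed range, gives:

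| Setting | Without | One extra | Two extra |
|---|---|---|---|
| One region, n=30 | 5/30 = 16.7% (5.6 to 34.7) | 6/30 = 20.0% (7.7 to 38.6) | 7/30 = 23.3% (9.9 to 42.3) |
| Part C, n=25 | 6/25 = 24.0% (9.4 to 45.1) | 7/25 = 28.0% (12.1 to 49.4) | 8/25 = 32.0% (14.9 to 53.5) |

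Each patient adds 1/30 = 3.3 points or 1/25 = 4.0 points. If 1 to 3 of all 85 expansion patients were affected, again an assumption, the pooled shift would be 1/85 = 1.2 to 3/85 = 3.5 points.

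**The case against.** The strongest reply is that the plan never says a response after progression counts; the result comes from silence. Table A-2 does not award PR to a sequence beginning with PD. The protocol presents response after initial growth as its reason for the immune-related criteria, and the duration definition presupposes that response comes before progression. On this view the negative duration shows that the reading was not intended, and a programmer would notice it. That is fair as to intent. It does not supply a rule: the one window stated runs past progression, and the SAP leaves it there.

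The second reply concerns weight. The study is mainly descriptive and sized for preliminary estimation. The 5/30 interval is already 34.7 - 5.6 = 29.1 points wide, and the Part B futility look is complete. This stands, and it limits the priority of the point.

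Two stronger readings are tempting and are not supported:

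- A reader might infer that every patient with pseudoprogression enters the RECIST 1.1 ORR. Table A-1 rules this out while a new lesion persists.
- A reader might infer that responses confirmed after the last dose are lost. The ORR definitions (Protocol 7.10.1.2 and 9.5, SAP 5.1.1) ask only for confirmation at least 28 days later and set no end-of-treatment limit. End of treatment is not defined as the last dose. Appendices 1 and 2 schedule a disease assessment at the End of Treatment visit, which Protocol Table 6 places 28 days after the last dose.

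What remains of the second reading is a lack of clarity. Suppose a patient is last dosed on day 22 and shows a first PR on day 43. The End of Treatment visit falls near day 22 + 28 = 50, but confirmation needs day 43 + 28 = 71 or later. Protocol 8.3 makes that visit optional. Scans continue in follow-up ("Disease assessment will be done at office follow-up visits until end of study if patient agrees"), but the text does not say whether they can confirm a response.

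**Conclusion.** The point holds in a limited form. As written, the RECIST 1.1 best-response window lets progression without a persisting new lesion, followed by confirmed shrinkage, count as a RECIST 1.1 response. This conflicts with PFS and DoR for the same patient. Each such patient moves ORR by 3.3 points at n=30 and 4 points at n=25. The documents give no count or rate of such patients, so the total effect cannot be determined and may be small.

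The conclusion rests on applying Appendix 7 literally; the documents do not direct that such responses be counted. It does not support a claim that the RECIST 1.1 ORR is broadly inflated or that late confirmations are dropped. It should be fixed, because the gap lies in the definition of a primary-objective measure and is cheap to close.

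**What to change.** In SAP 5.1.1 and 6.6.1, and in Appendix 7, state that RECIST 1.1 best overall response and its confirmation are derived from all assessments, on or off drug, from first dose up to the first RECIST 1.1 progression or the start of alternative anti-cancer therapy, whichever is earlier. Later assessments count only toward irRECIST. The words on or off drug also settle whether follow-up scans can confirm a response.

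If Appendix 8 is aligned, its window should end at confirmed irPD, consistent with the confirmation rule in SAP 5.1.1, or at new therapy. Ending it at the first unconfirmed irPD time point would remove the example patient's irRECIST response, since +22% at week 6 already meets the Appendix 8 time-point threshold for irPD.

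The cost is one sentence in each place and a programming rule on data already collected. Patient care does not change. The RECIST 1.1 ORR may come out slightly lower.

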Appendix 8 Immune-Related RECIST Guidelines

[Adapted from Wolchok 2009 (82)]

All patients will be required to have at least 1 measurable lesion to be considered as having measurable disease at baseline for the determination of eligibility for this study. Measurable lesions are defined below.

MEASURABILITY OF TUMOR AT BASELINE

DEFINITIONS

At baseline, tumor lesions/lymph nodes will be categorized measurable or non-measurable as follows:

Measurable

Tumor lesions: Must be accurately measured in at least one dimension (*longest* diameter in the plane of measurement is to be recorded) with a *minimum* size of:

- 10 mm by CT scan (CT scan slice thickness no greater than 5 mm).
- 10 mm caliper measurement by clinical exam (lesions which cannot be accurately measured with calipers should be recorded as non-measurable).
- 20 mm by chest X-ray.

Malignant lymph nodes: To be considered pathologically enlarged and measurable, a lymph node must be ≥ 15 mm in *short* axis when assessed by CT scan (CT scan slice thickness no greater than 5 mm). At baseline and in follow-up, only the *short* axis will be measured and followed. See also notes below on ‘Baseline documentation of target and non-target lesions’ for information on lymph node measurement.

Non-measurable

All other lesions, including small lesions (longest diameter < 10 mm or pathological lymph nodes with ≥ 10 to < 15 mm short axis) as well as truly non-measurable lesions. Lesions considered truly non-measurable include: leptomeningeal disease, ascites, pleural or pericardial effusion, inflammatory breast disease, lymphangitic involvement of skin or lung, abdominal masses/abdominal organomegaly identified by physical exam that is not measurable by reproducible imaging techniques.

Special considerations regarding lesion measurability

Bone lesions, cystic lesions, and lesions previously treated with local therapy require particular comment:

Bone lesions:

- Bone scan, PET scan or plain films are not considered adequate imaging techniques to measure bone lesions. However, these techniques can be used to confirm the presence or disappearance of bone lesions.
- Lytic bone lesions or mixed lytic-blastic lesions, with identifiable soft tissue components, that can be evaluated by cross sectional imaging techniques such as CT or MRI can be considered as measurable lesions if the soft tissue component meets the definition of measurability described above.
- Blastic bone lesions are non-measurable.

Cystic lesions:

- Lesions that meet the criteria for radiographically defined simple cysts should not be considered as malignant lesions (neither measureable nor non-measurable) since they are, by definition, simple cysts.
- ‘Cystic lesions’ thought to represent cystic metastases can be considered as measurable lesions, if they meet the definition of measurability described above. However, if non-cystic lesions are present in the same patient, these are preferred for selection as target lesions.

Lesions with prior local treatment:

- Tumor lesions situated in a previously irradiated area, or in an area subjected to other loco-regional therapy, are not considered measurable unless there has been demonstrated progression in the lesion prior to study enrollment.

SPECIFICATIONS BY METHODS OF MEASUREMENTS

Measurement of lesions

All measurements should be recorded in metric notation, using calipers if clinically assessed. All baseline evaluations should be performed as close as possible to the treatment start and **never more than 4 weeks before the beginning of the treatment.**

Method of assessment

The same method of assessment and the same technique should be used to characterize each identified and reported lesion at baseline and during follow-up. Imaging based evaluation should always be done rather than clinical examination unless the lesions(s) being followed cannot be imaged but are assessable by clinical exam.

Clinical lesions: Clinical lesions will only be considered measurable when they are superficial and ≥ 10 mm diameter as assessed using calipers (e.g. skin nodules). For the case of skin lesions, documentation by color photography including a ruler to estimate the size of the lesion is suggested. As noted above, when lesions can be evaluated by both clinical exam and imaging, imaging evaluation should be undertaken since it is more objective and may also be reviewed at the end of the study.

Chest X-ray: Chest CT is preferred over chest X-ray, particularly when progression is an important endpoint, since CT is more sensitive than X-ray, particularly in identifying new lesions. However, lesions on chest X-ray may be considered measurable if they are clearly defined and surrounded by aerated lung.

CT, MRI: CT is the best currently available and reproducible method to measure lesions selected for response assessment. This guideline has defined measurability of lesions on CT scan based on the assumption that CT slice thickness is 5 mm or less. When CT scans have slice thickness greater than 5 mm, the minimum size for a measurable lesion should be twice the slice thickness. MRI is also acceptable in certain situations (e.g. for body scans).

Ultrasound: Ultrasound is not useful in assessment of lesion size and should not be used as a method of measurement. Ultrasound examinations cannot be reproduced in their entirety for independent review at a later date and, because they are operator dependent, it cannot be guaranteed that the same technique and measurements will be taken from one assessment to the next. If new lesions are identified by ultrasound in the course of the study, confirmation by CT or MRI is advised. If there is concern about radiation exposure at CT, MRI may be used instead of CT in selected instances.

Endoscopy, laparoscopy: The utilization of these techniques for objective tumor evaluation is not advised.

Tumor markers: Tumor markers will not be used to assess *objective* tumor response.

TUMOR RESPONSE EVALUATION

ASSESSMENT OF OVERALL TUMOR BURDEN AND MEASURABLE DISEASE

To assess objective response or future progression, it is necessary to estimate the *overall tumor burden at baseline* and use this as a comparator for subsequent measurements. Only patients with measurable disease at baseline should be included. Measurable disease is defined by the presence of at least one measurable lesion (as detailed above).

BASELINE DOCUMENTATION OF ‘TARGET’ AND ‘NON-TARGET’ LESIONS

Where more than one measurable lesion is present at baseline all lesions up to a maximum of five lesions total (and a maximum of two lesions per organ) representative of all involved organs should be identified as *target lesions* and will be recorded and measured at baseline. For example, in instances where patients have only one or two organ sites involved, a maximum of two and four lesions respectively will be recorded). Target lesions should be

selected on the basis of their size (lesions with the longest diameter), be representative of all involved organs, but in addition should be those that lend themselves to *reproducible repeated measurements*. It may be the case that, on occasion, the largest lesion does not lend itself to reproducible measurement in which circumstance the next largest lesions which can be measured reproducibly should be selected.

Lymph nodes merit special mention since they are normal anatomical structures which may be visible by imaging even if not involved by tumor. As noted previously, pathological nodes which are defined as measurable and may be identified as target lesions must meet criterion of a short axis of ≥ 15 mm by CT scan. Only the *short axis* of these nodes will contribute to the baseline sum. The short axis of the node is the diameter normally used by radiologists to judge if a node is involved by solid tumor. Nodal size is normally reported as two dimensions in the plane in which the image is obtained (for CT scan this is almost always the axial plane; for MRI the plane of acquisition may be axial, sagittal or coronal). The smaller of these measures is the short axis. For example, an abdominal node which is reported as being 20 mm x30 mm has a short axis of 20 mm and qualifies as a malignant, measurable node. In this example, 20 mm should be recorded as the node measurement. All other pathological nodes (those with short axis ≥ 10 mm but < 15 mm) should be considered non-target lesions. Nodes that have a short axis < 10 mm are considered non-pathological and should not be recorded or followed.

A *sum of the diameters* (longest for non-nodal lesions, short axis for nodal lesions) for all target lesions will be calculated and reported as the *baseline sum diameters*. If lymph nodes are to be included in the sum, then as noted above, only the *short axis* is added into the sum. The baseline sum diameters will be used as reference to further characterize any objective tumor regression in the measurable dimension of the disease.

All other lesions (or sites of disease) including pathological lymph nodes should be identified as *non-target lesions* and should also be recorded at baseline. Measurements are not required and these lesions should be followed as ‘present’, ‘absent’, or in rare cases ‘unequivocal progression’. In addition, it is possible to record multiple non-target lesions involving the same organ as a single item on the case record form (e.g. ‘multiple enlarged pelvic lymph nodes’ or ‘multiple liver metastases’).

RESPONSE CRITERIA

This section provides the definitions of the criteria used to determine objective tumor response for target lesions by immune-related response criteria.

Evaluation of target lesions

Immune-Related Complete Response (irCR): Disappearance of all target lesions. Any pathological lymph nodes (whether target or non-target) must have reduction in short axis to <10 mm.

Immune-Related Partial Response (irPR): at least a 30% decrease in the sum of diameters of target lesions, taking as reference the baseline sum diameters.

Immune-related Progressive Disease (irPD): at least a 20% increase in the sum of diameters of target lesions, taking as reference the *smallest sum on study* (this includes the baseline sum if that is the smallest on study). In addition to the relative increase of 20%, the sum must also demonstrate an absolute increase of at least 5 mm.

Unlike conventional RECIST criteria, the appearance of new measurable lesions does not automatically denote disease progression under immune-related response criteria. Rather the dimensions of new measurable lesions are added to overall sum of tumor diameters for determination of objective response status. Patients will not be considered as having progression unless the new overall sum of diameters has increased by $\geq 20\%$ from the smallest sum of tumor diameters achieved while on study.

Immune-Related Stable Disease (irSD): Neither sufficient shrinkage to qualify for PR nor sufficient increase to qualify for PD, taking as reference the smallest sum diameters while on study.

Special notes on the assessment of target lesions

Lymph nodes. Lymph nodes identified as target lesions should always have the actual short axis measurement recorded (measured in the same anatomical plane as the baseline examination), even if the nodes regress to below 10 mm on study. This means that when lymph nodes are included as target lesions, the ‘sum’ of lesions may not be zero even if complete response criteria are met, since a normal lymph node is defined as having a short axis of <10 mm. In order to qualify for irCR, each node must achieve a short axis <10 mm. For irPR, irSD and irPD, the actual short axis measurement of the nodes is to be included in the sum of target lesions.

Target lesions that become ‘too small to measure’. While on study, all lesions (nodal and non-nodal) recorded at baseline should have their actual measurements recorded at each subsequent evaluation, even when very small (e.g. 2 mm). However, sometimes lesions or lymph nodes which are recorded as target lesions at baseline become so faint on CT scan that the radiologist may not feel comfortable assigning an exact measure and may report them as being ‘too small to measure’. When this occurs it is important that a value be recorded on the case report form. If it is the opinion of the radiologist that the lesion has likely disappeared, the measurement should be recorded as 0 mm. If the lesion is believed to be present and is faintly seen but too small to measure, a default value of 5 mm should be assigned (*Note*: It is less likely that this rule will be used for lymph nodes since they usually have a definable size when normal and are frequently surrounded by fat such as in the retroperitoneum; however, if a lymph node is believed to be present and is faintly seen but too small to measure, a default value of 5 mm should be assigned in this circumstance as well). This default value is derived from the 5 mm CT slice thickness (but should not be changed with varying CT slice thickness). The measurement of these lesions is potentially non-reproducible, therefore providing this default value will prevent false responses or progressions based upon measurement error. However, if the radiologist is able to provide an actual measure, that should be recorded, even if it is below 5 mm.

Lesions that split or coalesce on treatment. When non-nodal lesions ‘fragment’, the longest diameters of the fragmented portions should be added together to calculate the target lesion sum. Similarly, as lesions coalesce, a plane between them may be maintained that would aid in obtaining maximal diameter measurements of each individual lesions. If the lesions have truly coalesced such that they are no longer separable, the vector of the longest diameter in this instance should be the maximal longest diameter for the ‘coalesced lesion’.

Evaluation of non-target lesions

This section provides the definitions of the criteria used to determine the tumor response for the group of non-target lesions. While some non-target lesions may actually be measurable, they need not be measured and instead should be assessed only *qualitatively* at the time points specified in the protocol.

Immune-Related Complete Response (irCR): Disappearance of all non-target lesions. All lymph nodes must be non-pathological in size (<10mm short axis).

Non-CR/Non-PD: Persistence of one or more non-target lesions(s).

Immune-Related Progressive Disease (irPD): Unlike conventional RECIST 1.1, new measurable lesions or increases in the size of non-target lesions do not define PD in isolation in the immune-related response criteria. Rather, immune-related PD is established if the sum of diameters is $\geq 20\%$ of the nadir of the sum of diameters for a given patient.

New Lesions

The appearance of new malignant lesions alone does not denote disease progression. Instead, the diameter of new lesions is added to the sum of diameters for target and non-target lesions.

EVALUATION OF BEST OVERALL RESPONSE

The best overall response is the best response recorded from the start of the study treatment until the end of treatment taking into account any requirement for confirmation. The patient’s best overall response assignment will depend on the findings of both target and non-target disease.

Time point response

It is assumed that at each protocol specified time point, a response assessment occurs. For patients experiencing irCR or irPR, a confirmatory scan obtained no less than 4 weeks after the original scan is required to confirm the objective response. For patients experiencing irPD, but who demonstrate acceptable tolerability of treatment as evaluated by the investigator, a confirmatory scan obtained no less than 4 weeks after the original scan is required for the confirmation of irPD.

Immune-related response determination per irRECIST

Target Lesions	Non-Target Lesions	%Change Tumor Burden	Immune-Related Response Status
CR	CR	-100%	irCR
PR	Any	≤-30%	irPR
PR	Any	≥-30% to <+20%	irSD
PR	Any	≥+20%	irPD
SD	Any	≥-30% to <+20%	irSD
SD	Any	≥+20%	irPD
PD	Any	≥+20%	irPD

No new lesions allowed to achieve irCR status. Otherwise, presence or absence of new measurable or new non-measurable lesions does not affect response status in isolation. New measurable lesions added to cumulative tumor burden to calculate % change tumor burden for the determination of immune-related response status.

Immune-Related Complete Response (irCR): Complete disappearance of all target and non-target lesions and no new lesions. The short axis of all lymph nodes must be ≤ 10 mm.

Immune-Related Partial Response (irPR): The sum of diameters has decreased ≥ 30% from the baseline, but does not meet the criteria for irCR.

Immune-Related Stable Disease (irSD): The patient does not meet criteria for irCR, irPR or irPD.

Immune-Related Progressive Disease (irPD): The sum of diameters for target lesions and new measurable lesions has increased by ≥ 20% from the nadir sum of diameters

Missing assessments and inevaluable designation

When no imaging/measurement is done at all at a particular time point, the patient is not evaluable (NE) at that time point. If only a subset of lesion measurements are made at an assessment, usually the case is also considered NE at that time point, unless a convincing argument can be made that the contribution of the individual missing lesion(s) would not change the assigned time point response.

Best overall response: all time points

The *best overall response* is determined once all the data for the patient is known.

Complete or partial responses may be claimed only if the objective response is confirmed on a follow-up scan obtained no less than 4 weeks after the initial scan demonstrating an objective response. Absent this subsequent radiographic confirmation, irCR or irPR designations will be considered as unconfirmed responses.

Special notes on response assessment

